### 1.1 Study design

This is a multicenter, randomized, double-blind, placebo-controlled, parallel-group trial assessing the efficacy and safety of secukinumab 300 mg in two different dosing regimens in patients with biopsy-proven forms of lichen planus.

The study consists of three cohorts (one cohort per lichen planus subtype: cutaneous lichen planus (CLP), mucosal lichen planus (MLP) and lichen planopilaris (LPP)) and 4 study periods.

Patients are assigned to one of the three cohorts based on their **predominant** subtype and undergo a biopsy to confirm the clinical diagnosis at the screening visit:

- **Predominantly cutaneous** lichen planus
- **Predominantly mucosal** lichen planus
- **Lichen planopilaris**

Each cohort will follow the same study design across the 4 periods:

- **Screening Period:** up to 4 weeks prior to baseline
- **Treatment Period 1:** baseline to Week 16
- **Treatment Period 2:** Week 16 to Week 32
- **Follow-up:** 8 weeks after Week 32

#### **Screening period:**

A screening period of up to 4 weeks is used to assess patient's eligibility for the trial and to washout/ adjust prohibited medications. The screening period covers the time from the signature of informed consent/screening visit (-4 weeks) to the randomization visit (Week 0).

#### **Treatment Period 1:**

Treatment Period 1 is placebo-controlled and covers the time from Week 0 (randomization visit) to Week 16. Patients who meet all eligibility criteria are randomized in a 2:1 ratio to one of the following two treatment arms **within** their cohort:

- **Secukinumab 300 mg every 4 weeks (Q4W) arm:** subjects receive a weekly induction treatment from baseline to Week 4 followed by secukinumab 300 mg every 4 weeks.

- **Placebo for 16 weeks followed by secukinumab 300 mg every 2 weeks (Q2W) arm:** subjects receive matching placebo injections.

Thirty-six patients will be randomized per cohort, 24 to active and 12 to placebo treatment, which means that the study will enroll approximately 108 subjects in total.

In Treatment Period 1 all subjects receive weekly subcutaneous injections of blinded study drug (either 300 mg secukinumab or placebo) at Weeks 0, 1, 2, 3 and 4. Thereafter the frequency of blinded study drug injections for all subjects is every 4 weeks up to Week 16. Home administration of study drug is **not** allowed during Treatment Period 1, except for the case of a pandemic. Subjects who complete Treatment Period 1 roll over to Treatment Period 2 at the Week 16 visit. The only exception are subjects from the placebo for 16 weeks followed by secukinumab 300 mg every 2 weeks arm, who achieve spontaneous remission at the Week 16 visit. Spontaneous remission is defined as an IGA of 0 or 1 at Week 16. These subjects do **not** proceed to Treatment Period 2 to avoid unnecessary treatment. Instead, they will directly enter the Follow-up Period after the Week 16 visit.

### **Treatment Period 2:**

Treatment Period 2 starts at the Week 16 visit and covers the time until the Week 32 visit.

Depending on the treatment arm, subjects receive the following treatments:

- **Secukinumab 300 mg Q4W arm:** subjects receive continued treatment with secukinumab 300 mg every 4 weeks plus matching placebo injections to maintain treatment blinding.
- **Placebo for 16 weeks followed by secukinumab 300 mg Q2W arm:** subjects are switched to active treatment with secukinumab 300 mg **every 2 weeks** including a weekly induction starting from Week 16 to Week 20, with the exception of subjects achieving remission by Week 16.

The Week 16 injection is the first injection of Treatment Period 2.

Treatment remains blinded during Treatment Period 2. This means that starting at the Week 16 visit all subjects receive an induction consisting of weekly blinded study drug injections (either secukinumab 300 mg or placebo) at Weeks 16, 17, 18, 19 and 20, followed by blinded study drug injections every 2 weeks.

**The last study drug injection is administered at Week 30.** The end of Treatment Period 2 is Week 32. After Week 32, all subjects enter the Follow-up Period.

Subjects who discontinue study treatment prematurely for any reason other than withdrawal of informed consent should **not** be considered as discontinued from the study. Subjects should continue attending planned site visits and perform study assessments until the last visit of the treatment period during which they discontinue (Week 16 or Week 32).

[figure not shown]
Subjects, whether they are willing to continue attending further study visits or not, should attend the End of Treatment visit (EOT) during which they discontinued (EOT 1 for discontinuation

during Treatment Period 1 and EOT 2 for discontinuation during Treatment Period 2). EOT 1 should be performed 4 weeks after the last dose of study drug, and EOT 2 should be performed 2 weeks after last dose of study drug.

### Follow-up:

There is an 8-week Follow-up Period after Week 32. The End of Study (EOS) is reached at Week 40. If a subject discontinues study during Follow-up period, visit Week 40 has to be performed.

**Figure 1-1 Study design**

The primary endpoint will be evaluated at Week 16, where Week 16 represents a widely used and well-accepted timing for the assessment of key endpoints in several inflammatory skin diseases such as psoriasis, hidradenitis suppurativa or atopic dermatitis, as well as an established timepoint to detect the efficacy of secukinumab. The total study duration, up to 32 weeks of treatment, allows the collection of long-term efficacy and safety data beyond 16 weeks of treatment. Subjects who have been on placebo treatment in Treatment Period 1 are switched to active treatment with secukinumab 300 mg every 2 weeks (starting with the regular weekly induction). This enables placebo treated patients to receive active treatment during the trial as well. Furthermore, it allows the assessment of efficacy and safety of the 2-weekly dosing regimen in lichen planus.

The purpose of this primary endpoint analysis is to assess whether secukinumab shows efficacy and safety in the selected lichen planus subtypes at an early time point (proof of concept). This

enables planning of further clinical development of secukinumab in lichen planus. At the end of the study, a final analysis will be performed once all patients have completed their last study visit. All patients, investigators and site personnel will remain blinded until the final database lock.

Further analyses are currently not planned. However, an unscheduled analysis could be conducted if a compelling reason arises, for example, if requested by health authorities.

[figure not shown]
## 1.2 Study objectives and endpoints

[figure not shown]
The purpose of this proof of concept study is to elucidate the efficacy of secukinumab in the treatment of adult patients with biopsy-proven lichen planus not adequately controlled by topical therapies and to assess the safety and tolerability over 32 weeks.

[figure not shown]
**Table 1-1 Objectives and related endpoints.**

Objective(s)	Endpoint(s)
Primary objective(s)	Endpoint(s) for primary objective(s)

To demonstrate the clinical efficacy of secukinumab 300 mg every 4 weeks (Q4W) in subjects with cutaneous lichen planus (CLP), mucosal lichen planus (MLP), or lichen planopilaris (LPP) inadequately controlled by topical therapies, with respect to improvement in Investigator's Global Assessment (IGA) response by Week 16, compared to placebo.

	

Achievement of IGA response at Week 16 Patients diagnosed with biopsy-proven forms of CLP, MLP or LPP will be considered responders if they achieve an absolute IGA score ≤2 at Week 16

Secondary objective(s)	Endpoint(s) for secondary objective(s)

The secondary objectives of this trial comprise the following:

- evaluate the efficacy of secukinumab 300 mg Q4W compared to placebo throughout 16 weeks in Treatment Period 1;

- evaluate the long term efficacy of secukinumab 300 mg Q4W throughout 32 weeks in Treatment Period 2;

- evaluate the efficacy of secukinumab 300 mg Q2W in Treatment Period 2;

- evaluate the safety profile of secukinumab 300 mg throughout the duration of the study.

Detailed assessments are described the next section.

	
All subtypes	
Investigator's Global Assessment (IGA)	

Achievement of at least 2 points improvement from baseline in the IGA score at Week 16 and 32, and throughout the duration of the study

Achievement of IGA 0/1 score at Week 16 and 32, and throughout the duration of the study

Objective(s)	Endpoint(s)

• Dermatology Life Quality Index (DLQI)

	

• Absolute and relative change in DLQI from baseline to Week 16 and 32, and throughout the duration of the study

• Achievement of DLQI 0/1 score at Week 16 and 32, and throughout the duration of the study, among the subset of subjects with DLQI <math>\geq 2</math> at baseline

• Patient assessment of itch (NRS)

	

• Absolute and relative change in NRS from baseline to Week 16 and 32, and throughout the duration of the study



• Patient assessment of pain (NRS)

	

• Absolute and relative change in NRS from baseline to Week 16 and 32, and throughout the duration of the study

• To assess the safety and tolerability of secukinumab in subjects with lichen planus.

	

• Adverse events, laboratory values, vital signs

Cutaneous Lichen Planus (CLP)	

• Physician Assessment of Surface Area of Disease (PSAD) for Skin Disease

	

• Absolute and relative frequencies in PSAD from baseline to Week 16 and 32, and throughout the duration of the study

Mucosal Lichen Planus (MLP)	

• Reticular Erythematous Ulcerative (REU) score

	

• Absolute and relative change in REU score from baseline to Week 16 and 32, and throughout the duration of the study

• Oral Lichen Planus Symptoms Severity Measure (OLPSSM) score

	

• Absolute and relative change in OLPSSM score from baseline to week 16 and 32, and throughout the duration of the study

Lichen Planopilaris (LPP)	

• LPP Activity Index (LPPAI)

	

• Absolute and relative change in LPPAI score from baseline to Week 16 and 32, and throughout the duration of the study

• SCALPDEX Questionnaire

	

• Absolute and relative change in SCALPDEX Questionnaire score from baseline to Week 16 and 32, and throughout the duration of the study

## 2 Statistical methods

### 2.1 Data analysis general information

Novartis will be performing the analysis. Statistical software SAS version 9.4 or later will be used.

All data will be analyzed separately for each cohort (predominantly CLP, predominantly MLP, LPP), unless specified otherwise.

Summary statistics for continuous variables will include N, mean, standard deviation, minimum, lower quartile, median, upper quartile, maximum. Summary statistics for discrete variables will be presented in contingency tables and will include absolute and relative frequencies.

All listings will be presented by cohort and treatment groups.

Footnotes in the outputs will be kept to a minimum.

Footnotes will generally be provided for

- abbreviations used in the output; abbreviations used on several outputs, e.g. for listings in [\[Appendix 16.2\]](#) can be presented on a separate page and do not have to be repeated as footnotes on each listing
- sorting order of categories, e.g. for sorting within MedDRA (Medical Dictionary for Regulatory Activities) hierarchy levels
- MedDRA version used for reporting of MedDRA coded data

Footnotes will generally NOT be given for

- units displayed on the output
- interpretation of results (e.g. “odds ratio larger 1 favors active treatment”)
- information that can be retrieved from the statistical section of the clinical study report (CSR) unless it is not identifiable from the output, e.g.
  - explanation of analysis model used unless results of more than one model are displayed in an output
  - derivations of variables (e.g. BMI will not be explained in a footnote)
- information that will be provided in the clinical study protocol and/or methods section of the CSR (e.g. baseline definition if this is specified in the statistical section of the CSR)

#### 2.1.1 General definitions

##### 2.1.1.1 Study Day 1 and other study days

The first day of administration of randomized study treatment (first dose) is defined as *Study*

*Day 1 or Day 1.*

All other study days will be labeled relative to Day 1. For event dates on or after Day 1, study day for an event date is calculated as Date of event – [Day 1] + 1, i.e., Day 2, Day 3, etc., will be one day, two days, etc., after Day 1, respectively. For event dates before Day 1, study day for an event date is calculated as Date of event – [Day 1], i.e., Day -1, Day -2, etc., will be one day, two days, etc., before Day 1, respectively. Duration of an event will be calculated as (Event end date – Event start date + 1).

The descriptor “Day 0” will not be used.

### **2.1.1.2 Screening, baseline and post-baseline definitions**

*Screening* refers to any procedures (e.g., checking inclusion and exclusion criteria) performed prior to the first dose of study treatment. Per protocol, subject informed consent must be obtained prior to performing any study related activity. The date of signing informed consent is the start date of screening period. Any assessment obtained during the screening period will be labeled screening assessment. Assessments made on Day 1 may occur before or after the first dose.

For *efficacy* analyses, baseline is the last assessment (including unscheduled visits) obtained on or before the randomization day. All assessments obtained after randomization are considered as post-baseline unless otherwise specified.

For *safety* analyses, baseline is the last assessment (including unscheduled visits) obtained (on or) before the first dose (day) of study treatment. All assessments obtained after the first dose (day) of study treatment are considered as post-baseline unless otherwise specified.

Of note, baseline will be derived based on randomization day or first dose day, exact randomization or dosing time is not considered.

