## 2 Objectives and endpoints

**Table 2-1 Objectives and related endpoints**

Objective(s)	Endpoint(s)
Primary objective(s)	Endpoint(s) for primary objective(s)

 
To demonstrate the clinical efficacy of secukinumab 300 mg every 4 weeks (Q4W) in subjects with cutaneous lichen planus (CLP), mucosal lichen planus (MLP), or lichen planopilaris (LPP) inadequately controlled by topical therapies, with respect to improvement in Investigator's Global Assessment (IGA) score by Week 16, compared to placebo.
 
	
 
Achievement of IGA response at Week 16 Patients diagnosed with biopsy-proven forms of CLP, MLP or LPP will be considered responders if they achieve an absolute IGA score ≤2 at Week 16
 

Secondary objective(s)	Endpoint(s) for secondary objective(s)

 
The secondary objectives of this trial comprise the following: 
 
- evaluate the efficacy of secukinumab 300 mg Q4W compared to placebo throughout 16 weeks in Treatment Period 1;
 
- evaluate the long term efficacy of secukinumab 300 mg Q4W throughout 32 weeks in Treatment Period 2;
 
- evaluate the efficacy of secukinumab 300 mg Q2W in Treatment Period 2;
 
- evaluate the safety profile of secukinumab 300 mg throughout the duration of the study.
 
 
Detailed assessments are described the next section.
 
 
	
All subtypes Investigator's Global Assessment (IGA)	
 
Achievement of 2 points improvement in the IGA score from baseline to Week 16 and 32, and throughout the duration of the study Achievement of IGA 0/1 at Week 16 and 32, and throughout the duration of the study
 

Objective(s)	Endpoint(s)

• Dermatology Life Quality Index (DLQI)

	

• Absolute and relative change in DLQI from baseline to Week 16 and 32, and throughout the duration of the study

• Achievement of DLQI 0/1 score at Week 16 and 32, and throughout the duration of the study

• Patient assessment of itch (NRS)

	

• Absolute and relative change in NRS from baseline to Week 16 and 32, and throughout the duration of the study

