#### **Treatment Period 1:**

Treatment Period 1 is placebo-controlled and covers the time from Week 0 (randomization visit) to Week 16. Patients who meet all eligibility criteria are randomized in a 2:1 ratio to one of the following two treatment arms **within** their cohort:

- **Secukinumab 300 mg every 4 weeks arm:** subjects receive a weekly induction treatment followed by secukinumab 300 mg every 4 weeks.
- **Placebo for 16 weeks followed by secukinumab 300 mg every 2 weeks arm:** subjects receive matching placebo injections.

Thirty-six patients will be randomized per cohort, 24 to active and 12 to placebo treatment, which means that the study will enroll approximately 108 subjects in total.

In Treatment Period 1 all subjects receive weekly subcutaneous injections of blinded study drug (either 300 mg secukinumab or placebo) at weeks 0, 1, 2, 3 and 4. Thereafter the frequency of blinded study drug injections for all subjects is every 4 weeks up to Week 16. Home administration of study drug is **not** allowed during Treatment Period 1. Subjects who complete Treatment Period 1 roll over to Treatment Period 2 at the week 16 visit. The only exception are subjects from the placebo for 16 weeks followed by secukinumab 300 mg every 2 weeks arm,

who achieve spontaneous remission at the Week 16 visit. Spontaneous remission is defined as an IGA of 0 or 1 at Week 16. These subjects do **not** proceed to Treatment Period 2 to avoid unnecessary treatment. Instead they will directly enter the Follow-up Period after the Week 16 visit.

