### 5.1 Inclusion criteria

Subjects eligible for inclusion in this study must meet **all** of the following criteria:

1. Written informed consent must be obtained before any assessment is performed.
2. Female and male patients  $\geq 18$  years of age.
3. Subjects must have biopsy-confirmed forms of cutaneous lichen planus (CLP), mucosal lichen planus (MLP), or active lichen planopilaris (LPP) eligible for systemic therapy based on the following criteria:
  - rated IGA of  $\geq 3$  at screening and baseline (moderate or severe) **AND**
  - inadequate response to topical corticosteroids of high-ultrahigh potency in the opinion of the investigator.
4. If using any of the allowed topical treatments on the affected areas, the dose and application frequency should remain stable for 2 weeks prior to randomization and until Week 16.

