#### **Treatment Period 2: Weeks 16-32**

- Patients in the active **secukinumab 300 mg every 4 weeks treatment arm** stay on secukinumab 300 mg every 4 weeks, meaning they receive secukinumab 300 mg s.c. at Weeks 16, 20, 24 and 28. In order to maintain the blinding they additionally receive placebo injections at Weeks 17, 18 and 19 as well as placebo injections at Weeks 22, 26 and 30.
- Patients from the **placebo with switch to secukinumab 300 mg every 2 weeks treatment arm** switch over to active secukinumab 300 mg every 2 weeks treatment. They receive a weekly induction with secukinumab 300 mg s.c. at Weeks 16, 17, 18, 19 and 20 and then secukinumab 300 mg every 2 weeks, meaning at Weeks 22, 24, 26, 28 and 30.

The first injection of Treatment Period 2 is given at Week 16. The last injection (secukinumab 300 mg or placebo) is given in both the treatment arms **at week 30**.

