## **2.2 Analysis sets**

The following analysis sets will be used for the data analysis. Rules of exclusion criteria of analysis are detailed in [Section 5.6](#).

The **Randomized Analysis Set (RAS)** consists of all randomized subjects. Subjects will be analyzed according to the treatment assigned at randomization.

The **Full Analysis Set (FAS)** comprises all subjects to whom study treatment has been assigned. Subjects will be analyzed according to the treatment assigned to at randomization. Mis-randomized subjects (mis-randomized in IRT) will be excluded from FAS. Mis-randomized subjects are defined as cases where IRT contacts were made by the site either prematurely or

inappropriately prior to confirmation of the subject's final randomization eligibility and no study medication was administered to the subject.

The **Safety Set** includes all subjects who received at least one dose of study treatment. Subjects will be analyzed according to the study treatment received, where treatment received is defined as the randomized/assigned treatment if the subject took at least one dose of that treatment or the first treatment received if the randomized/assigned treatment was never received.

The summary statistics analyses in this study will be performed according to domains with respective specifications of analyses sets, analyses period and treatment groups ([Table 2-1](#)).

**Table 2-1** Summary statistics specifications

Domains	Analyses sets	Analysis Period	Treatment group labels for each analysis period
Patient disposition, Demographics, Other baseline characteristics *	RAS	Treatment Period 1	Secukinumab 300 mg Q4W Placebo Total
		Treatment Period 2 Follow up (only for disposition tables)	Secukinumab 300 mg Q4W Secukinumab 300 mg Q2W Total
Efficacy endpoints	FAS	Treatment Period 1	Secukinumab 300 mg Q4W Placebo
		Entire treatment period	Secukinumab 300 mg Q4W Placebo Placebo-Secukinumab 300 mg Q2W
Safety data (Number of doses, duration of exposure, prior and concomitant therapies, concomitant medical procedures, significant non-drug therapies, laboratory data, AEs, etc.)	Safety set	Treatment Period 1	Secukinumab 300 mg Q4W Placebo
		Entire treatment period	Secukinumab 300 mg Q4W Secukinumab 300 mg Q2W Placebo Any Secukinumab

\* Treatment groups for protocol deviations for entire treatment period: AIN457 300 mg Q4W, AIN457 300 mg Q2W, Any AIN457 300 mg, Placebo, Total

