#### Investigator's Global Assessment (IGA)

The following IGA related endpoints are considered:

- **IGA  $\geq 2$  points improvement response:** defined as achieving an  $\geq 2$  IGA score decreasing compared with baseline (thus at least achieving an IGA score of  $\leq 2$ ).
- **IGA 0 or 1 response:** defined as achieving an IGA score of 0 or 1 (thus at least achieving an IGA  $\geq 2$  points improvement)

For IGA  $\geq 2$  points improvement response and IGA 0 or 1 response from Week 1 to Week 16, comparisons between the 300 mg Q4W treatment regimen and placebo groups will be conducted using the Fisher exact test. Estimates of the difference of response rates between the 300 mg Q4W treatment regimen and placebo groups together with 95% confidence intervals will be presented.

Summary statistics for IGA  $\geq 2$  points improvement and IGA 0 or 1 response by visit from baseline up to the end of study for each treatment group will be presented in contingency tables with the number and percentage of subjects in each category.

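### Placebo-to-Q2W switchers' change scores run from Week 0; a descriptive table from a switch baseline would serve the Period 2 Q2W objective better

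*SAP*

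**What the plan says.** - **Baseline.** SAP 2.1.1.2, for efficacy: "baseline is the last assessment (including unscheduled visits) obtained on or before the randomization day". Everything after randomisation is post-baseline unless another rule is given, and none is visible. The derivation uses the day, not the time of dosing.
- **Protocol endpoints.** Protocol Table 2-1 words the endpoints in the same way, for example "Absolute and relative change in DLQI from baseline to Week 16 and 32, and throughout the duration of the study".
- **Start of Q2W.** Protocol 6.1.3 on the placebo arm in Treatment Period 2: "They receive a weekly induction with secukinumab 300 mg s.c. at Weeks 16, 17, 18, 19 and 20".
- **Objective.** SAP Table 1-1 lists as a secondary objective to "evaluate the efficacy of secukinumab 300 mg Q2W in Treatment Period 2".
- **Who switches.** Protocol section 3: "Spontaneous remission is defined as an IGA of 0 or 1 at Week 16". Placebo patients in remission go to follow-up and do not receive Q2W.
- **Reporting.** SAP 2.6.1 summarises absolute and percentage change from baseline, by visit to the end of the study, for DLQI, itch and pain NRS, REU, OLPSSM, LPPAI and Scalpdex. IGA improvement of at least 2 points is also counted from baseline. The LPPAI response categories are instead defined relative to pretreatment values.
- **Columns.** For efficacy over the entire treatment period, SAP Table 2-1 lists a Placebo column and a "Placebo-Secukinumab 300 mg Q2W" column and defines neither.
- **After discontinuation.** SAP 2.6.3 replaces data after treatment discontinuation, through Week 32, with the patient's baseline value. Other missing values are left as observed.
- **Switch-day provision.** SAP 2.4.2 says the first secukinumab dose day must be considered for visit windows in the placebo arm. It does not extend this to baseline.

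**The concern.** For patients who stay on Q4W, change from Week 0 is change since their regimen began. For switchers it is change since 16 weeks before their regimen began, so a Week 32 result adds a placebo phase to a Q2W phase. A patient who goes from IGA 4 to IGA 2 on placebo already counts as a 2-point responder before any Q2W dose, and still switches because only IGA 0 or 1 stops the switch.

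At stake is how well the descriptive Period 2 output answers the Q2W objective. Protocol 4.1 also intends to set Q2W in Period 2 beside Q4W in Period 1, and the two change scores would start from different points.

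**Working it through.** **1. The plan's own figure.** SAP section 3 gives a 71% probability of a positive proof of concept (0.712 in Table 3-1) for 24 versus 12 patients and response rates of 50% versus 20%. I enumerated all binomial outcomes with Beta(1/3, 1/3) priors and required both criteria, Pr(δ > 0) > 90% and Pr(δ > 0.15) > 50%. The result is 0.712, and all 20 table cells checked agree to three decimals. The figure uses Week 16 IGA ≤ 2 only, so the switch baseline does not touch it.

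**2. How many patients.** At most 12 per cohort switch. With assumed remission and dropout of 0 to 20% each (neither rate is documented), the number runs from 12 down to 12 × 0.8 × 0.8 = 7.7. At the plan's 20% placebo rate, 12 × 0.2 = 2.4 placebo patients per cohort are expected at IGA ≤ 2 by Week 16. The chance of at least one is 1 - 0.8^12 = 93%. Those at exactly IGA 2 switch; the split between IGA 2 and IGA 0/1 is not given.

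**3. Change scores.** Assume a score of 10 at Week 0 and 5 at Week 32. From Week 0 the change is -5 (-50%) whatever happened on placebo. From the switch:

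| Week 16 value | Change | Percent change |
|---|---|---|
| 10 | -5 | -50% |
| 9 | -4 | -44% |
| 8 | -3 | -38% |
| 7 | -2 | -29% |

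**4. What subtraction recovers.** In a fixed set of switchers who all stay on treatment, mean change at Week 32 minus mean change at Week 16 is the mean Period 2 change. Two features of the plan weaken this.

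- The columns are undefined, so the Week 16 mean may include placebo patients who never switched.
- Suppose a switcher with placebo change c stops Q2W. The Week 32 value is replaced by the Week 0 value, so the difference becomes 0 - c = -c. With the switch value as replacement it would be 0. The mean shifts by c/12 (8.3% of c), or by c/10 with 10 switchers.

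**5. Spread.** Suppose the Week 0-16 and Week 0-32 changes have equal SD s and correlation r (neither is documented). The SD of the Week 16-32 change is then s × √(2(1 - r)): 1.26s at r = 0.2, 1.00s at r = 0.5, 0.63s at r = 0.8. The planned summaries do not show which applies.

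**6. LPPAI categories, only if pretreatment means Week 0.** After a fractional fall p on placebo, the further fall needed to reach the 25% partial-response limit is 1 - 0.75/(1 - p). That is 16.7% for p = 0.10, 6.25% for p = 0.20, 0% for p = 0.25, and 37.5% after a 20% rise. Scores of 6.0, 4.8 and 4.2 at Weeks 0, 16 and 32 are a 30% reduction from Week 0 (partial responder) and 12.5% from the switch (non-responder). If pretreatment means before secukinumab, the limit is simply 25% from the switch.

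**7. IGA.** SAP 2.6.1 calls IGA 0/1 response "defined as achieving an IGA score of 0 or 1 (thus at least achieving an IGA" improvement of at least 2 points. Switchers have Week 0 IGA 3-4 and Week 16 IGA 2-4. Ending at 0 or 1 gives 2 × 3 × 2 = 12 possible paths. All 12 are 2-point improvements from Week 0, but 3-2-1 and 4-2-1 are not from Week 16. A 2-point response from the switch would therefore break the SAP's implication. IGA 0/1 among switchers is cleaner, because none of them was at 0/1 when Q2W began.

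**The case against.** The strongest reply is that nothing is wrong. The protocol defines its endpoints from baseline, the SAP reports them as defined, and Period 2 is descriptive in at most 12 patients per cohort. That stands: this is an improvement, not a correction.

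Other parts of the reply also stand:

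- **LPPAI.** A reader might infer that the LPPAI categories are fixed at Week 0. The documents do not support that. They refer to pretreatment values, which for a switcher could mean before placebo or before secukinumab.
- **Lost information.** A reader might infer that the Period 2 change cannot be obtained. It can: SAP 2.4.2 foresees efficacy listings by visit and period, and line plots are planned for some scales. But these do not summarise the SD or the percent change from the switch.
- **Redaction.** A reader might infer that the sponsor has no switch baseline. SAP Amendment 3 added analyses for the final report, and several of its items are blacked out. The point covers visible text only.
- **Size.** The spreads and shifts above rest on assumed inputs. A reader might infer that Q2W will look too good, but the direction of the placebo change is unknown.
- **Selection.** Excluding Week 16 remitters leaves a group selected for higher scores at that visit, so change from the switch is open to regression to the mean.

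The core remains. The visible planned summaries do not separate Q2W from the placebo phase, although the objective names Period 2.

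**Conclusion.** The point holds as a low-cost improvement to descriptive secondary output. For switchers, the listed change scores and the IGA 2-point improvement combine 16 weeks of placebo with Q2W. The LPPAI category reference is ambiguous for them. Subtracting visit means gives the mean Period 2 change only in a fixed set of switchers without discontinuation.

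The actual size cannot be stated, because no placebo change, correlation or dropout rate is documented; the numbers are illustrations. The primary endpoint, the 71% figure, IGA 0/1 and PSAD counts do not change. DLQI 0/1 is left as planned. Confidence is medium, because redacted text may already cover this.

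**What to change.** Keep all Week 0 summaries, and:

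- **Add to SAP 2.1.1.2:** *For placebo-arm subjects who start secukinumab, a second efficacy baseline is the last assessment on or before the day of the first secukinumab dose and within the Week 16 visit window; if there is none, it is missing.* The window is Days 100-127 in SAP Table 2-3. State that scheduled same-day assessments count as pre-dose, since Protocol 6.7.2 places them before the injection. Align the windows with the first-secukinumab-dose provision in SAP 2.4.2.
- **Report, in switchers only,** absolute and percent change from this baseline in DLQI, itch and pain NRS, REU, OLPSSM, LPPAI and Scalpdex at each scale's scheduled Period 2 visits. In this table, use the switch baseline for the SAP 2.6.3 replacement.
- **LPPAI:** state which reference pretreatment values means for switchers, and show the categories from the switch baseline.
- **IGA:** rely on IGA 0/1 among switchers plus their Week 16 IGA distribution.
- **SAP Table 2-1:** define the two placebo columns.
- **Label the table** descriptive and uncontrolled, with at most 12 selected patients per cohort. Say that it is not like-for-like with Q4W in Period 1 (where entry required IGA 3 or more), and that it is open to regression to the mean because Week 16 remitters are excluded.

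Cost: SAP wording, one derived baseline and one set of descriptive tables per cohort. No new data are needed, because Protocol Table 8-1 already schedules these scales at Week 16.
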